9.7.1.1 Primary Endpoint

The primary endpoint for the investigative phase of the study is the sum of bladder pain intensity differences from baseline to 12 hours (SPID-12) after administration of URG101 compared with the SPID-12 after administration of lidocaine alone, heparin alone, and placebo as determined by using the 11-point NRS for bladder pain.

9.7.1.2 Secondary Endpoints

The secondary endpoints of the study are:

1. The sum of bladder pain intensity differences from baseline to 24 hours (SPID-24) after administration of URG101 compared with lidocaine alone, heparin alone, and placebo as determined by using the 11-point bladder pain NRS
2. The sum of urgency intensity differences from baseline to 12 and 24 hours (SUID-12 and SUID-24) after administration of URG101 compared with lidocaine alone, heparin alone, and placebo using the 11-point urgency NRS
3. Absolute and percentage change in bladder pain from baseline to 1, 12, and 24 hours after administration of URG101 compared with lidocaine alone, heparin alone, and placebo as determined by using the 11-point NRS for bladder pain
4. Absolute and percentage change in urgency intensity from baseline to 1, 12, and 24 hours after administration of URG101 compared with lidocaine alone, heparin alone, and placebo using the 11-point urgency NRS
5. Patient Global Assessment: Comparison of the percentage of subjects achieving $\geq 50\%$ improvement in the PORIS questionnaire, Question 3, from baseline to 1 hour, 12 hours and 24 hours after administration of URG101, lidocaine alone, heparin alone, and placebo
6. Time to first administration of rescue medication for pain after treatment with URG101 compared to alkalinized Lidocaine Hydrochloride Injection (20 mg/mL) alone, alkalinized Heparin Sodium Injection (5,000 USPU/mL) alone, and placebo [REDACTED])
7. To evaluate the safety and tolerability of intravesical administration of URG101

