	
Pharmacokinetic Endpoints:
 
 1. Comparison of plasma lidocaine concentrations at 1 hour post treatment with absolute and percentage change in pain using the 11-point NRS for bladder pain at 1, 12 and 24 hours after administration of URG101, lidocaine alone, heparin alone, and placebo 2. Comparison of plasma lidocaine concentrations at 1 hour post treatment with absolute and percentage change in urgency using the 11-point NRS for urgency, at 1, 12 and 24 hours after administration of URG101, lidocaine alone, heparin alone, and placebo 3. Comparison of plasma lidocaine concentrations at 1 hour post treatment with the sum of bladder pain intensity differences from baseline to 12 and 24 hours (SPID-12 and SPID-24) after administration of URG101 compared with lidocaine alone, heparin alone, and placebo as determined by using the 11-point bladder pain NRS 4. Comparison of plasma lidocaine concentrations at 1 hour post treatment with the sum of urgency intensity differences from baseline to 12 and 24 hours (SUID-12 and SUID-24) after administration of URG101 compared with lidocaine alone, heparin alone, and placebo as determined by using the 11-point urgency NRS 
Safety Endpoints:
 
 1. Change from baseline in INR at 1 hour after study drug administration

CLINICAL PROTOCOL SYNOPSIS (continued)

	
2. Change from baseline in aPTT at the 1-hour post-study-drug time point 3. Adverse events
 
Pharmacokinetics: Samples for peak plasma lidocaine concentrations will be collected at baseline and at 1 hour after study drug administration.
 
Efficacy:
 
 • 11-point (i.e., 0 to 10) NRS bladder pain (numerical rating scale) • 11-point (i.e., 0 to 10) NRS urge (urgency intensity) to urinate (numerical rating scale) • PORIS questionnaire 
Safety: The following safety parameters will be evaluated:
 
 • Clinical laboratory tests • Vital sign measurements • Physical examination • Incidence of adverse events, serious adverse events • INR and aPTT 
Follow-up will occur for subjects with clinically significant, study drug-related abnormalities at the conclusion of the study termination visit, based on the investigators discretion.

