9.0 INVESTIGATIONAL PLAN

9.1 OVERALL STUDY DESIGN AND PLAN

This is a phase 2a, prospective, randomized, double-blind, placebo-controlled, multicenter, single-dose, pharmacokinetic study designed to determine the efficacy and safety of the combination product (URG101) versus its alkalinized individual components (Heparin Sodium and Lidocaine Hydrochloride) and placebo [REDACTED]
[REDACTED].

In this study, alkalinized Lidocaine Hydrochloride Injection (20 mg/mL) and alkalinized Heparin Sodium Injection (5,000 USP U/mL) will be subsequently referred to by the drug names alkalinized Lidocaine and alkalinized Heparin.

Eligible subjects exhibiting interstitial cystitis symptoms who have signed informed consent, will be screened and provisionally enrolled for intravesical treatment. Treatment may occur on the day of the Screening Visit (Visit 1) or any following day up to 1 week (Baseline and Drug Administration, Visit 1a). **If drug administration occurs on same day as screening then all assessments in Visit 1 and Visit 1a will be combined.** Confirmation of symptom severity must be obtained before randomization: minimum pain score of 5 on the 11-point numerical rating scale [NRS] at Screening and 15 minutes (\pm 5 minutes) after voiding prior to study drug administration. There is no minimum score requirement for the urgency NRS scales for patients to enter the study. Subjects will become fully enrolled upon receipt of acceptable qualifying laboratory evaluations and clinical assessments obtained before randomization.

On the day of study drug administration (V1a), subjects will be randomized (2:1:2:1; URG101:placebo:lidocaine:heparin) and will receive a single administration of one of four intravesical treatments in a blinded fashion, based on random assignment:

1. URG101 (buffered lidocaine-heparin)
2. Placebo: [REDACTED]
3. Lidocaine alone: [REDACTED]
4. Heparin alone: [REDACTED]

During the study, subjects will be allowed to take their protocol-allowed medications at their usual doses. Additionally, they may use only a short acting non-steroidal anti-inflammatory drugs (NSAIDs) as rescue medication, not sooner than 8 hours after receiving study medication and not within 6 hours prior to receiving study medication ([Table 1](#)).

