15. Evidence or suspected presence of cancer detected during cystoscopy prior to or at time of initial screening.
16. Has received any investigational drug or device within 30 days prior to screening
17. Is currently enrolled in another investigational drug or device study
18. Is unwilling or unable to abide by the requirements of the study
19. Have an actively bleeding lesion or area in the bladder as detected by dipstick urinalysis and investigator assessment, immediately prior to randomization ([Section 9.5.1.5](#). If the investigator determines that active bleeding is not occurring and that it is safe for the subject, the subject may continue in the study.)
20. Have had any of the following:
 - Bacterial cystitis within 30 days as demonstrated by a positive urine culture ($\geq 10^5$ bacteria per mL)
 - History of pelvic irradiation or radiation cystitis
 - History or presence of uterine, cervical, pelvic, rectal, ovarian or vaginal cancer
 - History of benign or malignant bladder tumors
 - Current chemotherapy
 - History or presence of tuberculous cystitis

- History or presence of chemical cystitis, including that due to cyclophosphamide
- History or presence of urinary schistosomiasis
- Bladder or ureteral calculi
- Clinically significant infectious vaginitis
- Currently uncontrolled genital herpes
- History or presence of urethral diverticulum
- Presence of bladder fistulae
- History of ketamine use

Immediately prior to receiving treatment of study drug, subjects will be re-evaluated as follows: Subjects will be asked to void; 15 minutes (\pm 5 minutes) after voiding, their urinary bladder volume will be measured to rule out diuresis by using an ultrasonic bladder scan or by inserting a catheter and collecting urine. The 11-point bladder pain NRS will also be administered at this time. Subjects will be excluded based on the following criteria:

- Score of < 5 on the 11-point bladder pain NRS (Note: No minimum is needed for urgency NRS.)
- [REDACTED]
- [REDACTED]
- [REDACTED]
- Significant urethral discomfort upon urethral catheterization

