9.4 TREATMENTS

9.4.1 Treatments Administered

The study drugs will be blinded and assigned to each subject based on the randomization schedule. The contents of each kit will be admixed immediately prior to administration by the investigator who will administer the drug to the patient at no colder than room temperature. The following treatments will be administered as a single dose via urethral catheter:

- URG101 treatment comprises the following:
 - 18 mL containing heparin sodium [REDACTED]
[REDACTED] Lidocaine HCl buffered to pH 7.4 (± 0.2) with 1X [REDACTED]
buffer, [REDACTED] [REDACTED]
[REDACTED]
[REDACTED]
- Placebo treatment comprises the following:
 - 18 mL 1X [REDACTED] buffer (pH 7.4 [± 0.2])
- Heparin treatment comprises the following:
 - 12 mL Heparin Sodium [REDACTED] plus 6 mL
3X [REDACTED] buffer (final mixture buffered to pH 7.4 [± 0.2])
- Lidocaine treatment comprises the following:
 - 12 mL Lidocaine HCl [REDACTED] plus 6 mL 3X [REDACTED] buffer
(final mixture buffered to pH 7.4 [± 0.2])

Prior to administering drug each subject will empty their bladder. Fifteen minutes later (± 5 minutes), the subject will complete the 11-point bladder pain NRS (requires a score of ≥ 5.0 to enter the trial and receive drug) and the 11-point urgency NRS (critical to administer 15 minutes (± 5 minutes) after voiding but no minimum score is required for study entry). These NRS scores will be the baseline scores for pain and

urgency. [REDACTED]

[REDACTED]

[REDACTED]

[REDACTED]

[REDACTED]

[REDACTED]

[REDACTED]

[REDACTED] The study medication is to be left indwelling for 45 minutes, with a minimum of 30 minutes, and after that may be voided by the subject. The test instruments will then be administered at the intervals listed in the schedule of assessments (Table 4).

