9.7.1.4 Pharmacokinetic Endpoints

Samples for plasma lidocaine concentrations will be collected at baseline and at 1 hour after study drug administration. The pharmacokinetic endpoints of the study are:

1. Comparison of plasma lidocaine concentrations at 1 hour post treatment with absolute and percentage change in pain using the 11-point bladder pain NRS, at 1, 12 and 24 hours after administration of URG101, lidocaine alone, heparin alone, and placebo.
2. Comparison of plasma lidocaine concentrations at 1 hour post treatment with absolute and percentage change in urgency using the 11-point urgency NRS, at 1, 12 and 24 hours after administration of URG101, lidocaine alone, heparin alone, and placebo.
3. Comparison of plasma lidocaine concentrations at 1 hour post treatment with the sum of bladder pain intensity differences from baseline to 12 and 24 hours (SPID-12 and SPID-24) after administration of URG101 compared with lidocaine alone, heparin alone, and placebo as determined by using the 11-point bladder pain NRS.
4. Comparison of plasma lidocaine concentrations at 1 hour post treatment with the sum of urgency intensity differences from baseline to 12 and 24 hours (SUID-12 and SUID-24) after administration of URG101 compared with lidocaine alone, heparin alone, and placebo as determined by using the 11-point urgency NRS.

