9.7.1.14 Efficacy Analyses

All SPID endpoints will be calculated using Simpson's trapezoidal rule. SPID will be calculated as follows, where n is the total number of time points within the time period with non-missing imputed PID values:

If multiple scores are recorded at the same date and time, the most conservative PI scores (highest) will be used.

Primary Efficacy Analyses

The primary efficacy analyses will be performed on the intent-to-treat set. As a sensitivity analysis, the primary efficacy analysis will also be performed on the PP set. Primary efficacy analyses will also be conducted on the per protocol set, which will include all subjects in the ITT set who sufficiently comply with the protocol.

The primary efficacy endpoint will be compared between the URG101 group and the lidocaine, heparin, and placebo groups using an analysis of covariance model including factors for site and randomized treatment assignment; baseline pain will be added to the model as a covariate. Pairwise comparisons of least squares means between URG 101 and the two active treatment arms, as well as the placebo arm, will be performed. The probability values will be derived using the contrast statement from the model. If the p-value associated with these comparisons is < 0.05 in favor of URG101, the primary aim of the trial will be confirmed.

Sites with small numbers of patients enrolled may be pooled for analysis. The method used to determine pooling will be specified in the statistical analysis plan and any pooling will be finalized and documented prior to database lock and unblinding.

Secondary Efficacy Analyses

Analyses of the secondary endpoints relating to changes in the pain and urgency NRS will be performed using analysis of covariance models similar to those used for the primary efficacy endpoint. The ITT set will be used. Nonparametric methodology in exploratory analyses may be used to supplement the parametric analyses.

Treatment differences based on the PORIS questionnaire, Question 3, will be analyzed by pairwise Cochran-Mantel-Haenszel Tests based on $\geq 50\%$ improvement of symptoms.

Time to first pain medication use will be analyzed using Kaplan-Meier methodolgy. Log-rank tests will be used to compare the treament groups.

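### Percentage change in urgency is a tested secondary endpoint, yet urgency has no entry minimum, so the measure may be undefined at baseline 0 and is unstable at low baselines

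*Combined protocol and SAP*

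**What the plan says.** Secondary endpoint 4 in Section 9.7.1.2 is "Absolute and percentage change in urgency intensity from baseline to 1, 12, and 24 hours", comparing URG101 with lidocaine, heparin and placebo. Section 9.7.1.4 uses the measure again in PK endpoint 2: "absolute and percentage change in urgency using the 11-point urgency NRS, at 1, 12 and 24 hours". Secondary objective 3 (synopsis and Section 8.2) and the synopsis endpoint lists carry matching text.

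On analysis, Section 9.7.1.14 states: "Analyses of the secondary endpoints relating to changes in the pain and urgency NRS will be performed using analysis of covariance models". The models are to resemble the primary one and use the ITT set. Nonparametric methods may be added as exploratory support.

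On entry, Section 9.1 states: "There is no minimum score requirement for the urgency NRS scales for patients to enter the study". Sections 9.3.2, 9.4.1 and 9.5.1.9 repeat this, while pain must be at least 5. Both scales run from 0 to 10. Section 9.4.1 fixes the denominator: of the ratings taken 15 minutes (± 5) after voiding and before dosing it says "These NRS scores will be the baseline scores for pain and" urgency.

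The missing-data rules that can be read in Section 9.7.2 cover rescue medication, withdrawal and diary gaps. None addresses a zero or very low baseline. Sections 9.7 and 9.7.1 leave further detail to a separate SAP, which is not among the supplied documents.

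**The concern.** The plan treats percentage change in pain and in urgency alike, but only pain has a floor. For urgency, a permitted baseline of 0 leaves the endpoint without a value, so the analysis would cover fewer subjects than the ITT set it names. Permitted baselines of 1 to 4 give a few subjects very large percentages, mostly in the direction of worsening, because improvement stops at −100%. Those subjects can dominate the residual variance and pull the treatment contrast.

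At stake are nine pairwise tests (three time points by three comparators) in one secondary endpoint, plus one PK endpoint. The same plan already lists better-behaved measures of urgency.

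**Working it through.** **1. The plan's own figure.** The synopsis states 90% power for SPID-12. With a two-sided 0.05 test and the normal approximation, power = Φ(d / √(1/n₁ + 1/n₂) − 1.96).
- URG101 v lidocaine, d = 0.60, 60 v 60: 0.60/0.1826 = 3.286, so Φ(1.326) = 90.8%.
- URG101 v placebo or heparin, d = 0.75, 60 v 30: 0.75/0.2236 = 3.354, so Φ(1.394) = 91.8%.

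The figure reproduces. It concerns pain; the plan gives none for urgency.

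**2. Can an eligible subject have baseline urgency 0?** Yes. The scale includes 0 and no urgency minimum applies. The synopsis population is defined by pain and/or urgency, and inclusion criterion 3 names only bladder pain. The PUF range (at least 15, below 30) does not force urgency either. The questionnaire's maximum is 35, and items 6, 7a and 7b contribute at most 3 each. With all three at 0 a total of 35 − 9 = 26 is still possible.

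**3. What the measure does at each baseline b.** Percentage change = 100 × (score − b)/b. One point is therefore 100/b, and the largest worsening is 100 × (10 − b)/b.

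| Baseline | One point | Possible range |
|---|---|---|
| 0 | undefined | none |
| 1 | 100% | −100% to +900% |
| 2 | 50% | −100% to +400% |
| 3 | 33% | −100% to +233% |
| 4 | 25% | −100% to +150% |
| 5 (pain floor) | 20% | −100% to +100% |
| 10 | 10% | −100% to 0% |

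**4. How many subjects might have no value.** The documents give no distribution, so one is assumed: normal, rounded and clipped to 0–10. The share at 0 is Φ((0.5 − mean)/SD).
- Mean 4.5, SD 2.5: Φ(−1.6) = 5.5%, about 10 of 180.
- Mean 5.5, SD 2.5: Φ(−2.0) = 2.3%, about 4 of 180.
- Mean 6.5, SD 2: Φ(−3.0) = 0.13%, fewer than 1 of 180.

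**5. Effect on power.** Simulated trials, 60 v 60, had a 1.2-point effect and residual SD 2 (1.2/2 = 0.60, the plan's effect size for URG101 v lidocaine). Scores were rounded and clipped. Both measures were analysed by ANCOVA with baseline as covariate, and percentage change left out baseline 0. With assumed discrete baseline distributions:

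| Baseline urgency | Absolute | Percentage | Loss (points) | SD of % change |
|---|---|---|---|---|
| Floor of 5, as for pain | 88.3% | 86.4% | 1.9 | 29 |
| 2% at zero | 87.1% | 82.0% | 5.1 | 41 |
| 5% at zero | 86.5% | 77.6% | 8.9 | 46 |
| 10% at zero | 83.0% | 72.7% | 10.3 | 54 |

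With normal baselines, mean 4.5 to 6.5 and SD 2 to 2.5, power is about 86–89% for absolute change and 71–84% for percentage change, a loss of roughly 4 to 16 points. The loss is smaller when baseline urgency is high and follow-up tracks baseline closely.

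**6. Which part does the damage.** Losing 5% of subjects alone, at d = 0.60 and 57 v 57, takes power from 90.8% to 89.3%, or 1.5 points. Most of the loss in step 5 therefore comes from the low non-zero baselines. It does not need zeros to be common.

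**The case against.** Four points on the other side deserve weight.

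- **Frequency is not documented.** The text shows that a zero baseline is allowed, not that it occurs. A reader might infer from the post-void timing that low scores will be common. No section says so. Section 7.1 calls frequency and urgency hallmarks of the disease, and PUF item 6 asks about urgency that remains after voiding. The timing argument is plausible but unproven, and this point does not rely on it.
- **A rule may exist elsewhere.** A zero-denominator convention is ordinary SAP detail, and a figure in Section 9.7.2.2 is not reproduced in the supplied text. Absence here does not prove absence from the plan. This limits the claim about a missing rule. A rule for zeros alone would still leave the instability at baselines 1 to 4.
- **Some protection is already present.** Rank-based methods would soften the effect of extreme percentages, but Section 9.7.1.14 offers nonparametric methods only as optional and exploratory.
- **Percentage change has a use.** Section 7.3 reports average percentage change in urge from URG101-104. Keeping the measure allows comparison with that study, which is a reason to keep it as a description.

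A reader might also infer that the trial's main conclusion or stated power is weakened. It is not: SPID-12 is a pain measure with baseline at least 5, and absolute urgency change, SUID-12 and SUID-24 are defined at every baseline.

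**Conclusion.** The point holds as a minor weakness in the choice of analysis. That the measure can be undefined for ITT subjects, and that it is unstable at low baselines, follows from the entry rules and arithmetic alone. The size does not: about 0.1% to 6% undefined and roughly 4 to 16 points of power lost rest on an assumed baseline mean of 4.5 to 6.5, SD 2 to 2.5, a 1.2-point effect and residual SD 2, at 60 v 60. Quoting only the unfavourable end would overstate it. The documents support saying that the measure may be undefined for some subjects, not that it will be. The direction was the same in every setting tried: percentage change had less power than baseline-adjusted absolute change.

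**What to change.** - For urgency, base hypothesis tests on absolute change at 1, 12 and 24 hours and on SUID-12 and SUID-24. State that baseline urgency is the covariate; Section 9.7.1.14 names only baseline pain, for the primary model.
- Report percentage change in urgency descriptively, for subjects at or above a baseline value fixed before unblinding, with the number excluded in each arm. The value is a judgement: a cut at 3 caps one point at 33%, a cut at 5 at 20% as for pain.
- Apply the same rule to PK endpoint 2, and align secondary objective 3 and the synopsis objectives and endpoints.
- If the separate SAP already has a rule for zero or low baselines, refer to it and check that it covers both.

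The cost is wording only: no new data and no change to conduct. Nine tests of a measure that overlaps with absolute change become descriptive. The one real loss is that comparison with the URG101-104 percentage-change result for urge is no longer inferential.

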9.7.1.3 Safety Endpoints

The safety endpoints of the study are:

1. Change from baseline in INR at 1 hour after study drug administration.
2. Change from baseline in aPTT at 1 hour after study drug administration.
3. Adverse events

9.7.1.4 Pharmacokinetic Endpoints

Samples for plasma lidocaine concentrations will be collected at baseline and at 1 hour after study drug administration. The pharmacokinetic endpoints of the study are:

1. Comparison of plasma lidocaine concentrations at 1 hour post treatment with absolute and percentage change in pain using the 11-point bladder pain NRS, at 1, 12 and 24 hours after administration of URG101, lidocaine alone, heparin alone, and placebo.
2. Comparison of plasma lidocaine concentrations at 1 hour post treatment with absolute and percentage change in urgency using the 11-point urgency NRS, at 1, 12 and 24 hours after administration of URG101, lidocaine alone, heparin alone, and placebo.
3. Comparison of plasma lidocaine concentrations at 1 hour post treatment with the sum of bladder pain intensity differences from baseline to 12 and 24 hours (SPID-12 and SPID-24) after administration of URG101 compared with lidocaine alone, heparin alone, and placebo as determined by using the 11-point bladder pain NRS.
4. Comparison of plasma lidocaine concentrations at 1 hour post treatment with the sum of urgency intensity differences from baseline to 12 and 24 hours (SUID-12 and SUID-24) after administration of URG101 compared with lidocaine alone, heparin alone, and placebo as determined by using the 11-point urgency NRS.

